	
To test for heterogeneity across strata, the exact test of Zelen will be performed testing whether the treatment effect differs between the 2 strata included in the primary analysis.
 
Progression-free survival will be analyzed using a stratified log-rank test using the Breslow method to handle ties (Breslow, 1974). The analysis will be stratified by primary tumor location (GB/Non-GB).
 
Overall survival will be analyzed using the methods outlined above for PFS. For Part 1, OS will be analyzed twice. A preliminary analysis of OS will be performed at the time of the primary analysis of ORR and PFS. It is anticipated that the OS data at this time will be immature, thus a second analysis of OS is planned for when approximately 95 patients (approx. 79%) have an OS event. The second analysis of OS will be considered the primary analysis of OS for Part 1 of the trial. For Part 2, the primary analysis of OS will be performed when 247 patients have experienced an OS event. Further details will be provided in the study SAP.
 
Duration of response will be listed and summarized descriptively for the duration of response in responding patients, including the associated Kaplan-Meier curves.
 
Disease control rate will be analyzed using the methods described above for ORR.
 
Tumor size is a secondary endpoint in Part 1 and will be used to assess the exploratory objective of evaluating the role of HER family expression levels as predictors of benefit to varlitinib. Tumor size will be analyzed by analysis of covariance (ANCOVA).
 
Plasma sampling will be conducted for population PK evaluation in Parts 1 and 2 of the study and will use an NLME. PK sampling of all patients is planned for Part 1 of the study while sparse PK sampling is planned for Part 2. For the sparse PK sampling in Part 2, the double-blind design will be maintained and blood samples will be collected from a selected number of patients without limiting the sampling to varlitinib patients only.
 
All PK data will be analyzed according to treatment received. Deviations that have the potential to significantly affect the PK will be reviewed. The population, and decisions regarding which profiles are usable, will be defined by the Study Team Physician, Pharmacokineticist, and Statistician prior to unblinding or any analyses being performed.
 
ECG/QT Analysis (Safety Lead-in and Part 1)
 
General Principles
 
Baseline will be defined as the mean of the triplicate ECG readings performed pre-dose on Day 1. On Day 1, pre-dose is defined as 2 sets of triplicate ECGs taken 45 minutes and 5 minutes prior to dosing. The ECG values from these 2 sets of ECGs will be averaged to create the baseline value. Similarly, for all other time points, for each ECG parameter, each patient's mean will be calculated from the triplicate readings and the mean value will be used.
 
The final ECG assessments (including interval measurements) will be made by the Core ECG laboratory. The Part 1 electrocardiographic Core ECG Laboratory assessments constitute the study's primary assessment of ECG/QTc. Any analysis of ECG data from the Safety lead-in is considered exploratory.
 
Due to the non-randomized, open label design of the Safety lead-in, data from the Safety lead-in will be presented separately from data from Part 1 of the study. Furthermore, ECG/QT outputs will be made available to the DSMB for consideration when determining whether the study should progress to Part 1.

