5.3 Selection of Study Population

5.3.1 Number of Planned Patients

Safety lead-in:

A total of 12 to 20 eligible patients will be enrolled to receive varlitinib plus capecitabine.

United States: 6 to 12 eligible patients are expected to be enrolled from the United States.

Rest of the World: An additional 6 to 8 eligible patients will be enrolled from the rest of the world.

Patients in this group will be replaced if investigational product compliance is < 85% in the first 14 days. Pharmacokinetic sampling will be performed in approximately 12 patients.

Part 1:

Approximately 120 eligible patients will be enrolled and randomized in a 1:1 ratio to receive varlitinib and capecitabine (n=60) or placebo and capecitabine (n=60).

Part 2:

Approximately 350 eligible patients will be enrolled and randomized in a 1:1 ratio to receive varlitinib and capecitabine (n=175) or placebo and capecitabine (n=175).

In both Part 1 and Part 2 of the study, patients will be stratified by:

- region - US and the rest of world (ROW) and;
- primary tumor location - gallbladder vs non-gallbladder.

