- Absolute heart rate, pulse rate, QRS, QT/QTc values at 45 minutes pre-dose, 5 minutes pre-dose, 1, 2, 3, 4, 5, 6, 8.5, and 12 hours post dose
- Heart rate, pulse rate, QRS, QT/QTc change from baseline at 1, 2, 3, 4, 5, 6, 8.5, and 12 hours post-dose

QTc will be reported for both Fridericia and Bazett's corrections.

Triplicate ECGs will also be collected 3 hours post-dose Day 22 (Cycle 2 Day 1) and onwards every cycle while the subject remains in the study.

Due to the non-randomized, open label design of the Safety lead-in, data from the Safety lead-in will be presented separately from data from Part 1 of the study. Furthermore, ECG/QT outputs will be made available to the DSMB for consideration when determining whether the study should progress to Part 1.

Part 1

The Part 1 electrocardiographic Core ECG Laboratory assessments constitute the study's primary assessment of ECG/QTc. The time-based electrocardiographic analysis will be performed in Part 1 at baseline, Cycle 1 Day 1, Cycle 1 Day 8, and safety follow-up visit.

On Cycle 1 Day 1 and Day 8, the following parameters will be determined at the following time points:

- Absolute heart rate, pulse rate, QRS, and QT/QTc values at 45 minutes pre-dose, 5 minutes pre-dose, 1.5, 3, 5, 8 hours post-dose.
- Heart rate, pulse rate, QRS, and QT/QTc change from baseline at 1.5, 3, 5, and 8 hours post-dose.

Twenty-eight days after the last dose of study drug (after full drug washout), a set of triplicate ECGs will be collected 3 hours after a light snack.

In addition, triplicate safety ECGs will be collected 3 hours post-dose on Day 22 (Cycle 2 Day 1), Day 64 (Cycle 4 Day 1) and every 2 cycles while the subject remains in the

study. This data will not be analyzed by the Core ECG Laboratory but will be assessed by the investigator.

Part 2

ECGs will be collected in Part 2 of the study as part of standard safety monitoring at screening, baseline (before a snack), and 3 hours post-dose on Day 22 (Cycle 2 Day 1), Day 64 (Cycle 4 Day 1) and every 2 cycles while the subject remains in the study. These data will not be analyzed by the Core ECG Laboratory but assessed by investigators.

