Following Part 1 of the study, a formal statistical analysis will be performed to assess the potential impact of varlitinib and capecitabine on changes in the ECG parameters.

The statistical stepwise approach will be used to separate the cardiodynamic effect of varlitinib from normal circadian fluctuation in the ECG values and from the effect of capecitabine:

1. ANOVA mixed effects comparison of the absolute values of ECG parameters at each time point vs baseline using treatment as a fixed effect in order to evaluate the contribution of circadian fluctuation and

to determine how treatment differences contribute to the changes. The ECG parameter values will be log-transformed and the resulting output will include the geometric mean ratio for test vs reference with the corresponding confidence interval and p-value. Interaction term, time point x treatment, will be also evaluated if the data allow.

2. ANOVA comparison of the absolute values of ECG parameters as well as change from baseline (Δ ECG) between treatments for each post-dose time point assessed separately in order to separate the varlitinib effect from that of capecitabine. The ECG parameter values will be log-transformed and the resulting output will include the geometric mean ratio for test vs reference with the corresponding confidence interval and p-value. Δ ECG will be tested as untransformed and log-transformed parameters to avoid bias from discarding 0 Δ ECG values from the comparisons.
3. Exposure-Response Analysis: Linear mixed effect model between Δ QTcF and time matched concentrations of varlitinib and other potential metabolites if measured and as appropriate. Other ECG variable may be similarly analyzed and other models used, if appropriate.
 - 3.1 Δ QTcF will be calculated as the difference between each time point value and the average baseline value for each arm with the combination varlitinib/capecitabine treatment.
 - 3.2 $\Delta\Delta$ QTcF will be calculated for each patient in the combination arm individually as the difference between the Δ QTcF value for the arm with combination varlitinib/capecitabine treatment and the average value of all patients in the capecitabine alone arm matching time point. Other ECG parameters may also be used in the analysis including QTcB, heart rate, etc to provide supporting information.
 - 3.3 Base linear mixed effect model will include patients as a random effect.

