 - 3.4 The total dose of capecitabine may be included as a fixed effect in the model to account for differences in total doses received by subjects with different body surface area.
4. Linear mixed effect model between Δ QTcF parameters and time matched concentrations of capecitabine and 5-FU (metabolite of capecitabine) and other potential metabolites if measured and as appropriate

- 4.1. $\Delta QTcF$ will be calculated for all patients in both arms as the difference between each time point value and the average baseline value.
- 4.2. Base linear mixed effect model will include patients as a random effect and treatment (capecitabine alone or in combination with varlitinib) as a fixed effect; the total capecitabine dose may also be used as a fixed effect.
5. Different covariates may be included in the complex models in addition to the base model as fixed effects such as time point in order to ensure the model feasibility and to evaluate covariates influential to ECG parameters.

The results of the fitted models will be presented using statistical parameters such as the geometric mean ratios and corresponding confidence intervals (for ANOVA) and estimates of the slope, and associated confidence interval for the linear mixed effect models.

In addition, the following graphic exploration of the exposure-ECG relationship may be performed:

- Residual plots to predict results
- Double Y plots with time on the X axis and time matched values of PK concentrations for varlitinib and capecitabine on the Y1 axis, ΔECG on the Y2 axis to determine the possibility of hysteresis between drug concentration and cardiodynamic effects
- Regression/scatter plots with time matched concentrations of varlitinib and capecitabine on the X axis and ΔECG on the Y axis
- Regression/scatter plots with varlitinib or capecitabine non-compartmental PK parameters of C_{max} , C_{trough} , AUC_{tau} and others on the X axis and maximum ΔECG on the Y axis
- Forest plots for different categories in ECG changes vs mean (SD) non-compartmental PK parameters for varlitinib or capecitabine on the X axis

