## 6.2 Adjustments for Covariates

It is planned that all statistical analyses will be stratified by geographical region (US/Non-US) and primary tumor location (GB/non-GB), in accordance with the stratification factors declared at randomization.

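### The Part 1 between-arm ECG comparison (step 2) fits no baseline covariate and names no main analysis; adding the averaged pre-dose baseline is a free, probably modest, gain in precision

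*Protocol*

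**What the plan says.** The formal ECG analysis of Part 1 is a numbered sequence of five steps, given in the protocol synopsis, in protocol 8.5.2.3 and in SAP 7.11.4.2. Step 2 compares the randomised arms directly. It is an "ANOVA comparison of the absolute values of ECG parameters as well as change from baseline", made "between treatments for each post-dose time point assessed separately in order to separate the varlitinib effect from that of capecitabine". All three places agree. Absolute values are analysed on the log scale and reported as geometric mean ratios. Change from baseline is analysed both untransformed and log-transformed. No covariate is named, and no result is identified as leading.

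A baseline is available for each patient. Two triplicate sets are taken before the first dose, and "The ECG values from these 2 sets of ECGs will be averaged to create the baseline value" (synopsis). Post-dose readings follow at 1.5, 3, 5 and 8 hours on Cycle 1 Days 1 and 8 (protocol 7.1.1.7). The same section states: "The Part 1 electrocardiographic Core ECG Laboratory assessments constitute the study's primary assessment of ECG/QTc".

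Three other places bear on covariates:
- Step 5 says "Different covariates may be included in the complex models in addition to the base model as fixed effects such as time point".
- SAP 6.2 names geographical region and primary tumour location for statistical analyses in general, and SAP 6.7 allows region to be dropped.
- The tumour-size ANCOVA (protocol 8.5.2.1, SAP 7.6) includes baseline tumour size as a covariate.

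**The concern.** With a baseline measured before dosing in a randomised comparison, the usual analysis fits that baseline as a covariate and lets the data estimate its slope. Step 2 instead fixes the slope at 0 (absolute values) or at 1 (change). Unless the true slope happens to equal the fixed value, precision is given away.

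Two consequences follow. First, intervals for the varlitinib effect on QTcF and the other ECG parameters are wider than the collected data require. Second, a chance difference between arms at baseline pushes the two analyses apart, and the plan does not say which to believe. This matters beyond reporting, because both documents make exposure-response modelling depend on whether varlitinib appears to have a meaningful ECG effect.

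**Working it through.** **No planned figure to reproduce.** The documents give no SD, correlation, effect size, alpha or power for the ECG comparison. The inputs taken from them are 60 patients per arm (protocol 5.3.1) and the 90% confidence level of the ECG summaries (protocol 8.5.2.3). The correlation r between baseline and post-dose value, and the SDs, are assumptions.

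**Does another passage supply the baseline term?**
- Step 5 is optional, its only example is time point, and the term base model appears only in the mixed models of steps 3 and 4.
- SAP 6.2 does not list the baseline value of the outcome.
- Step 1 compares each time point with baseline, so baseline is a level of the comparison, not a covariate. Its treatment-by-time interaction is fitted only if the data allow.

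So the term is not specified anywhere.

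**Variance of the arm difference, equal SDs, same scale.** In units of the absolute-value analysis:
- absolute values: 1
- change from baseline: 2(1 − r)
- ANCOVA: 1 − r²

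Hence ANCOVA/change = (1 − r²)/[2(1 − r)] = (1 + r)/2, and ANCOVA/absolute = 1 − r².

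| r | ANCOVA/change | CI narrower | change-score n per arm to match 60 | ANCOVA/absolute | CI narrower |
|---|---|---|---|---|---|
| 0.5 | 0.75 | 13% | 80 | 0.75 | 13% |
| 0.7 | 0.85 | 8% | 71 | 0.51 | 29% |
| 0.8 | 0.90 | 5% | 67 | 0.36 | 40% |
| 0.9 | 0.95 | 3% | 63 | 0.19 | 56% |

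A simulation of 10,000 trials with 60 per arm gave 0.74, 0.87 and 0.90 against change, and 0.78, 0.50 and 0.36 against absolute values, at r = 0.5, 0.7 and 0.8. Estimating the slope multiplies the ANCOVA variance by about 1 + 1/(120 − 4) = 1.009, so it costs under 1%.

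**Less variable baseline.** The baseline averages two triplicate sets and a post-dose value averages one, so its SD may be smaller. With an SD ratio of 0.9, the change-score variance is 0.81 + 1 − 1.8r:
- r = 0.5: 0.75/0.91 = 0.82, a saving of about 18%
- r = 0.7: 0.51/0.55 = 0.93, about 7%
- r = 0.8: 0.36/0.37 = 0.97, about 3%
- r = 0.9: 0.19/0.19 = 1.00, no saving, because the true slope is then 0.9/0.9 = 1

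**In milliseconds.** Assume a QTcF SD of 15 to 20 ms and r = 0.7. The 90% half-width for absolute values is 1.645 × SD × √(2/60), or 4.5 to 6.0 ms. For change it is 3.5 to 4.7 ms, and for ANCOVA 3.2 to 4.3 ms.

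**Chance imbalance.** Let D be the baseline difference between arms and b the true slope. Imbalance adds bD to the absolute contrast and (b − 1)D to the change contrast, so on one scale the two differ by exactly D. With the same assumed SDs at baseline, the standard error of D is SD × √(2/60) = 2.7 to 3.7 ms. ANCOVA gives one treatment estimate whether the response is the value or the change.

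**The case against.** A reader might infer that baseline is ignored altogether. It is not: the change analysis subtracts each patient's own baseline, and step 1's conditional interaction also draws on it. What is missing is an estimated slope.

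A reader might also infer that the planned contrasts are biased. They are not: under randomisation both are unbiased, and imbalance matters only for how close one trial's estimate lies to the truth.

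The gain is also easy to overstate. The large savings apply only against absolute values, which are always paired with the change analysis. Against change scores at higher correlations the saving is 10% to 5% of variance with equal SDs, and it can vanish if the baseline is less variable. In the illustration above it is worth about 0.3 to 0.4 ms of half-width.

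It is tempting to say that a test to exclude a QT effect is weakened. The documents set no margin or exclusion rule for step 2, and ECG effects are a Part 1 secondary objective. The label of primary ECG assessment covers the Part 1 Core ECG Laboratory data as a whole, in contrast with the exploratory Safety lead-in. It does not single out step 2.

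Finally, step 5 could be read as permitting a baseline term. Permission is not specification, and the term is not named there.

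These objections limit the size and the consequence. They do not supply the missing covariate or say which analysis leads.

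**Conclusion.** The point holds as an inexpensive improvement to the analysis, not as a flaw in validity. Step 2 fits no baseline covariate in any of its three statements and names no main analysis. In large samples ANCOVA is at least as precise as either planned analysis; with 120 patients the worst case is a loss under 1%.

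The saving in variance against change scores is 25% down to 5% for r from 0.5 to 0.9 with equal SDs, and about 18%, 7% and 3% at r = 0.5, 0.7 and 0.8 with an SD ratio of 0.9. Against absolute values it is 25% up to 81%. These figures rest on assumed correlations and SDs and on comparing analyses on one scale. The true values may differ by parameter and by day. The more certain gain is a single between-arm estimate that does not depend on which of two unadjusted analyses is read.

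**What to change.** Before unblinding, amend SAP 7.11.4.2 step 2, and align protocol 8.5.2.3 and the synopsis if they are next amended:
- Add the same parameter's averaged pre-dose baseline as a covariate, together with the stratification factor or factors retained in the analysis.
- Fit the model per time point, or as one repeated-measures model with treatment by time.
- Name the baseline-adjusted change from baseline, untransformed, as the main between-arm ECG analysis, reported as a difference with a 90% CI.
- Keep the absolute-value and geometric-mean-ratio outputs as supportive. They need not be dropped.

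Using the untransformed change also avoids a problem in the same step: a logarithm is undefined for zero or negative changes.

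The cost is SAP wording and one extra model term. No new data are needed.

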Statistical Analysis:	
Safety lead-in
 
All safety data will be listed and summarized using appropriate descriptive statistics. Full details will be provided in the statistical analysis plan (SAP).
 
The pharmacokinetic endpoints of varlitinib, capecitabine and 5-FU will be plotted and summarized using descriptive statistics.
 
QTcF exposure response modeling, along with time-based central tendency effects and categorical QTc analyses will be evaluated. Both the Bazett and Fridericia correction (primary correction method) formulae will be used to estimate QTc.
 
Parts 1 and 2
 
For Part 1 and 2, all primary and key secondary efficacy endpoints will be analyzed based on the Full Analysis Set (FAS) using an intention-to-treat principle. Patients who were randomized but did not subsequently go on to receive study treatment will be included in the FAS. Analyses performed in the protocol-defined "Evaluable for Response set (EFR)" will be supportive.
 
Objective response rate will be analyzed using a stratified exact binomial test (Mehta et al, Emerson) which extends Fisher's Exact test to more than one stratum. The analysis will be stratified by primary tumor location (GB/non-GB). The 2-sided p-value will be obtained by doubling the 1-sided p-values.

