8.5.2.3 ECG/QT Analysis

For the Safety lead-in, exploratory descriptive and categorical analyses, including change from baseline will be performed to investigate the impact of varlitinib and capecitabine treatments on the changes from baseline in ECG parameters.

For Part 1 of the study, a multi-step approach will be applied to evaluate the effect of capecitabine alone and varlitinib in combination with capecitabine on the ECG parameters at different time points post-dose. The comparisons will be done between ECG values at each time point post-dose and baseline and between treatment arms with and without varlitinib for each time point individually. The evaluation of the cardiodynamic effects of capecitabine and varlitinib may be explored using exposure-response modeling if there appears to be a meaningful effect of varlitinib when added to capecitabine on the ECG parameters including QTcF. This will be further described in the SAP.

Central Tendency Analysis will be performed for both the Safety lead-in and Part 1 of the study, the change from baseline in QTcF, PR, QRS, QTcB, and heart rate, will be summarized by time point (and treatment arm for Part 1) using descriptive statistics (n, mean, SD, min, median, max, 90% confidence intervals).

For both the Safety lead-in and Part 1, the following categorical data will be summarised:

- The proportion of patients obtaining treatment-emergent absolute QTcF values > 450 msec and \leq 480 msec; > 480 msec and \leq 500 msec; and > 500 msec
- The proportion of patients obtaining a QTcF increase from baseline values \geq 30 and <60 msec and \geq 60 msec
- The proportion of patients obtaining a QRS change from baseline > 25% resulting in QRS > 120 msec
- The proportion of patients obtaining a PR interval change from baseline >25% reaching a value >220 msec
- The proportion of patients obtaining a > 25% decrease from baseline in heart rate resulting in a heart rate < 50 beats per minute (bpm) or a > 25% increase from baseline in heart rate resulting in a heart rate > 100 bpm

For Part 1 of the study, the above categorical data summaries will be presented by treatment arm.

Following this, categorical analyses will be applied to the categorical data summaries above.

Additionally, T-wave morphology will be analyzed. The morphological T-wave analysis will be focusing on the change from baseline, i.e., treatment emergent changes.

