14.2.7.3	Summary of Plasma Pharmacokinetic Parameters – Varlitinib - PK Population
14.2.7.4	Summary of Plasma Pharmacokinetic Parameters – Capecitabine - PK Population (Parts 1 and 2)
14.2.8.1	Summary of IHC Biomarkers – FAS Population (Parts 1 and 2)
14.2.8.2	Shift Table of IHC Biomarkers from Baseline to Week 6 – FAS Population (Parts 1 and 2)
14.3.1.1	Summary Statistics for Exposure – Safety Population
14.3.1.2	Summary Statistics for Dose Intensity – Safety Population
14.3.2.1	Overview of TEAEs – Safety Population
14.3.2.2	Incidence of TEAEs by System Organ Class and Preferred Term – Subject and Episode Level – Safety Population
14.3.2.3	Incidence of Causally Related TEAEs by System Organ Class and Preferred Term – Subject and Episode Level – Safety Population
14.3.2.4	Incidence of most frequent (>10%) TEAEs by Preferred Term – Safety Population
14.3.2.5	Incidence of most frequent (>10%) Causally Related TEAEs by Preferred Term – Safety Population
14.3.2.6	Incidence of TEAEs CTCAE Grade 3 or Higher by System Organ Class and Preferred Term – Safety Population
14.3.2.7	Incidence of Causally Related TEAEs CTCAE Grade 3 or Higher by System Organ Class and Preferred Term – Safety Population
14.3.2.8	Incidence of serious TEAEs by System Organ Class and Preferred Term – Safety Population
14.3.2.9	Incidence of Serious Causally Related TEAEs by System Organ Class and Preferred Term – Safety Population
14.3.3	Summary of Deaths – Safety Population
14.3.4.16	Categorical Summary of Haematology Parameters – Safety Population (Parts 1 and 2)
14.3.4.17	Categorical Summary of Clinical Chemistry Parameters – Safety Population (Parts 1 and 2)

Table Number	Table Title
14.3.4.18	Categorical Summary of Urinalysis Parameters – Safety Population (Parts 1 and 2)
14.3.6.1	Absolute Values and Change from baseline in ECG Data – Safety Population
14.3.6.2	Categorical ECG Data Summaries – Safety Population
14.3.6.3	ECG Overall Evaluation by Visit – Safety Population
14.3.6.5	Comparison of ECG parameters at all visits to baseline by treatment – Safety Population
14.3.6.6	Comparison of ECG parameters at all visits between treatments – Safety Population
14.3.6.7	Comparison of ECG parameters at all visits between treatments – PK Population

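### The Part 1 ECG comparison tests change from baseline on a log scale that cannot hold decreases or zeros, and nothing says which of the two versions governs

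*Protocol*

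**What the plan says.** Examining the effect of varlitinib on ECG parameters is a Part 1 secondary objective (protocol 4.2). Protocol 8.5.2.3 sets out a stepwise analysis. Step 2 is an ANOVA between arms at each post-dose time point, applied both to the absolute ECG values and to ΔECG.

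- **Absolute values:** "The ECG parameter values will be log-transformed and the resulting output will include the geometric mean ratio for test vs reference".
- **ΔECG:** it "will be tested as untransformed and log-transformed parameters to avoid bias from discarding 0" values. The same sentence stands in the protocol synopsis and in SAP 7.11.4.2, Part 1, step 2.
- **Definition of the change:** given for QTcF in step 4.1, it "will be calculated for all patients in both arms as the difference between each time point value and the average baseline value". That is an arithmetic difference.
- **Decreases are expected:** one categorical summary counts patients with more than a "25% decrease from baseline in heart rate resulting in a heart rate" under 50 bpm.
- **Deferral:** of the Part 1 multi-step approach the protocol says "This will be further described in the SAP". On this point the SAP repeats the sentence unchanged.
- **What is called primary:** the correction formula ("Both the Bazett and Fridericia correction (primary correction method) formulae will be used to estimate QTc") and the Part 1 core-laboratory readings. Neither statement fixes the scale of the ΔECG test.
- **Outputs:** SAP 10.1 lists tables 14.3.6.6 (safety population) and 14.3.6.7 (PK population), both titled "Comparison of ECG parameters at all visits between treatments", with no scale named.

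**The concern.** The stated reason for running two versions is that the log would lose zeros. It overlooks that the log also loses every negative change, and those are far more numerous than exact zeros. A log-ΔECG test can use only patients whose value rose at that time point. Being retained then depends on the outcome, and retention differs between arms as soon as there is a treatment effect, so this test no longer compares the randomised groups.

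The plan gives this test the same formal place as the valid one and has no rule for disagreement. The result feeds a judgement: exposure-response modelling may follow if varlitinib appears to have a meaningful ECG effect. With two unranked tests, one of them selective and weaker, that judgement could be settled after unblinding by choosing between them.

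**Working it through.** **Is there a figure to reproduce?** No. The documents give no power, alpha or sample size for the ECG step 2 comparison. The defect follows from the definitions and needs no distributional assumption; the arithmetic below only shows scale.

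**1. Domain.** ΔECG = post-dose value − baseline. log(x) is undefined for every x ≤ 0. No offset, ratio or other device for negative changes appears in either document.

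**2. Could log-transformed ΔECG mean log(post-dose) − log(baseline)?** That quantity is defined for every patient. With an assumed baseline of 420 ms, changes of −20, 0 and +20 ms give −0.049, 0 and +0.047. But a zero on that scale is an ordinary value and would not be discarded. The plan's worry about discarding zeros makes sense only for the log of the raw difference, so its own rationale rules this reading out.

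**3. Illustration: inputs.** From protocol 5.3.1: 60 patients per arm. Assumed, because the documents are silent: normal ΔQTcF, the same SD in both arms (10, 15 or 20 ms), placebo mean −5, 0 or +5 ms, true difference 10 ms. This gives nine scenarios.

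**4. Formulas**, for mean μ and SD σ:
- share lost to the log = Φ(−μ/σ)
- mean among retained values = μ + σ·φ(μ/σ)/Φ(μ/σ)
- geometric mean among retained values = exp of the mean of log(x) given x > 0, by numerical integration
- power: 8,000 simulated trials per scenario, two-sided 5% t-test, all values untransformed against log of positive values only.

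**5. Central case (placebo mean 0, SD 15).**
- Placebo lost: Φ(0) = 50%, about 30 of 60. Varlitinib lost: Φ(−10/15) = 25%, about 15 of 60.
- Retained mean, placebo: 15 × 0.3989/0.5 = 11.97 ms.
- Retained mean, varlitinib: 10 + 15 × 0.3194/0.7475 = 16.41 ms.
- Difference among retained patients: 16.41 − 11.97 = 4.4 ms, against a true 10 ms.
- Retained geometric means: 7.9 and 11.8 ms, ratio 1.48 (from unrounded values).

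**6. Four of the nine scenarios.**

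| Placebo mean / SD (ms) | Lost, placebo / varlitinib | Difference among retained (ms) | Geometric mean ratio | Power, untransformed / log |
|---|---|---|---|---|
| −5 / 10 | 69% / 31% | 3.7 | 1.74 | 1.00 / 0.44 |
| 0 / 15 | 50% / 25% | 4.4 | 1.48 | 0.96 / 0.36 |
| +5 / 10 | 31% / 7% | 6.3 | 1.86 | 1.00 / 0.90 |
| −5 / 20 | 60% / 40% | 3.6 | 1.32 | 0.77 / 0.16 |

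**7. Across all nine.** Placebo values lost 31–69%; varlitinib values lost 7–40%; difference among retained values 3.6–6.3 ms; geometric mean ratio 1.32–1.86. Power is 77–100% untransformed and 16–90% for the log version, which is lower in every scenario.

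**The case against.** The strongest reply is that the plan already contains the remedy. Only the untransformed test keeps zeros, so the sentence can be read as adding it to guard against values the log discards. Nothing formal depends on which version governs: the multiplicity scheme in SAP 6.5 covers efficacy endpoints only, and the ECG comparison carries no alpha or margin. The neighbouring analyses are sound: the log of absolute values, untransformed change-from-baseline summaries, categorical thresholds in ms and plain ΔQTcF in the exposure-response models. With identical distributions in both arms, the log test rejected in about 4–6% of simulated trials (3,000 per scenario), so under these assumptions it does not invent a signal. The log test also reports a ratio, so the smaller millisecond difference among retained patients is not the figure it would print. Finally, SAP 10.1 lists only titles, and one table could show both versions.

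Much of this stands, and it limits the consequence. The intent to safeguard is plausible, the null behaviour is acceptable in the illustration, and the untransformed test keeps good power beside the log version. The table titles alone prove little.

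It does not remove the defect. The safeguard is never named as governing, and the rationale misses decreases altogether. The protocol's closing statement that ANOVA results will be shown as parameters such as geometric mean ratios leans, if anything, towards the log output. A formal between-arm test that discards patients by outcome should not be pre-specified just because a valid one stands next to it.

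**Conclusion.** The concern holds. As written, the log-transformed ΔECG test drops all decreases and zeros, does not compare the randomised groups when there is an effect, and has no stated rank against the untransformed test. That conclusion rests only on the definition of the change and the domain of the logarithm.

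The size depends on assumed means and SDs. Over the range shown, about a third to two thirds of placebo values would be lost at a time point, and power would fall from 77–100% to 16–90%. The practical risk is two conflicting between-arm ECG results with no rule to settle them, not a missed primary result. The problem is confined to one test within a Part 1 secondary objective; it should be corrected.

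**What to change.** In protocol 8.5.2.3 step 2, the matching synopsis text and SAP 7.11.4.2 step 2:

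- Delete the log-transformed ΔECG test, or replace it with log(post-dose/baseline), which is defined for every patient. The plan already takes this form for tumor size when normality is doubtful (protocol 8.5.2.1, SAP 7.6).
- Name untransformed ΔECG as the governing analysis, reported as the between-arm difference in original units (ms or bpm) with its confidence interval at each time point.
- Keep the log transform for absolute ECG values.
- In SAP tables 14.3.6.6 and 14.3.6.7, state the scale separately for absolute values and for ΔECG, since step 2 covers both.

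The cost is one clause in three places and two table titles. No added data, visits or patients are needed.
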